also complete surveys at the start of the study, at the one-month mark (mid intervention), the three month mark (end of intervention) and three months after the intervention is complete (follow up). Demographic information will be collected along with perceptions of PrEP, decisional conflict, and self-efficacy. Other moderators will also be collected. Compliance with PrEP will be assessed through self-report (in person and via text) and through either blood test or urine sample at one month, three months and six months. For recruitment and study timeline, see attachment A.

Study Timeline

We plan to begin the pilot RCT as soon as Institutional Review Board (IRB) approval is granted. We anticipate enrollment to take place between July through November, 2020 with follow-ups completed by March, 2021.

Inclusion/Exclusion Criteria

All participants must be self-identified women, 18 years of age or older, able to read and speak English, be HIV negative, self-report HIV risk behavior, report never taking PrEP, have a cell phone that accepts text messages, and must be a client of Prevention Point Philadelphia. They will also have to have health insurance (i.e. Medicaid). Individuals with mental illness that interferes with cognitive understanding or ability to provide informed consent will be excluded, with researchers trained to identify participants who exhibit signs of inability to meaningfully participate.

Inclusion Criteria

1. Woman-identified HIV negative client of Prevention Point Philadelphia
2. 18 of years of age or older
3. Self-report either sharing needles or having unprotected sex in the last 3 months
4. Speak and read English
5. Not have used PrEP previously
6. Have a working cell phone that receives text messages
7. Have health insurance

Recruitment

For this phase, we will recruit participants who are self-identified female clients of Prevention Point Philadelphia. Because Prevention Point received funds from the city, this protocol has also gone through review at the City of Philadelphia and been approved (see attached).

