Prevention Point Philadelphia (PPP). PPP is the only syringe exchange in Philadelphia. They promote health, empowerment and safety for communities affected by drug use and poverty by offering case management, syringe exchange, medical services, HIV and Hepatitis C (HCV) testing, addiction services, housing services, free meals, legal clinic and overdoes prevention and reversal training. PPP serves hundreds of people throughout the week, many of whom attend almost daily.

Sampling

Subjects will be screened for their interest in and eligibility for participating. We aim to enroll 68 women, assuming a 75% retention rate at the end of the intervention, leaving us a final study sample of 50. Treatment allocation will be accomplished using randomization through REDCap, a HIPAA approved research management software.

PROCEDURE PHASE 3

For graphic representation of study Procedure, see attached. Participants will be asked to participate after or while waiting for services at the study site. If they are interested, research staff will take participants into a designated private room and ask eligibility questions and be HIPAA consented. If they report that they meet the eligibility requirements, they will be taken to an HIV tester at Prevention Point Philadelphia for confirmation of status. If a woman tests positive for HIV, she will be provided regular counseling through PPP's testing program and given access to resources and services to link her to immediate care. If the woman does not have HIV and is eligible to be in the study, she will be consented into the study.

Once confirmed to be HIV-, participants will be randomized to a group using REDCap's randomization tool and a baseline survey will be conducted by research staff. All survey assessments will be orally administered to participants to address any literacy or cognitive issues. Responses will be entered into REDCap by a research staff member.

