Mosio will have no identifying information other than a participant’s phone number. Mosio will collect user data on the number of participants who open the text messages and will also resend text messages if they remain unopened for more than two days to assess feasibility. In addition, participants will be provided the opportunity to engage with study personnel if they have questions. A phone number will be provided in every text and study personnel will be available to take participant’s phone calls and answer their text messages. All messages/calls are sent to the study coordinator’s email and we will provide language that indicates that if questions are after business hours of 9 am to 5 pm we will answer the question the next morning. There will also be an opportunity to provide feedback. At mid-intervention participants will be asked to text back an answer to an adherence question. This provides an opportunity for participants to be actively engaged and to assess feasibility and acceptability. We will receive weekly reports from Mosio on which participants have opened text messages to assess feasibility.

At the end of the first month, all participants will also receive a text asking about their adherence to PrEP. They will respond with a 1 or 0 to indicate they have or have not taken PrEP the previous day. To help alleviate any problems with running out of cell phone minutes, every participant will receive a \$25 gift card to help pay for minutes needed. If they lose or have their cell phone stolen, we will assist them in getting a new one through the current services at PPP.

PPP has a current service that provided assistance to clients and we will work with them to help the study participant.

At the end of the first month we will also contact participants about completing a quick assessment of adherence and acceptability of the intervention. This will be done in person at Prevention Point. Similarly, at the end of the three-month intervention study staff will contact participants about completing a post-test assessment. We will attempt to correspond assessments to be at a time when they are already at Prevention Point and ideally meeting with their PrEP counselor or there for other services.

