Secondary outcomes. Secondary outcomes include self-efficacy, PrEP attitudes and decisional conflict. These measures are all continuous. Following evaluation of the primary outcome, we will explicitly examine the association between treatment adherence characteristics and extent of change among individuals in the treatment conditions in order to evaluate dose-response associations. Multiple linear models will be used to examine relationships between the groups and decisional conflict scale items, self-efficacy, and PrEP attitude scales at month three and three months post intervention. In these models, baseline outcome measures will be adjusted as covariate in the model development. PrEP attitudes will also be assessed through perceptual mapping analysis and compared from baseline to three month and three month follow-up for each group to assess "movement" toward adherence and away from negative perceptions of PrEP use. Promise of efficacy would indicate more movement by those in the "Enhanced" group compared to the "Basic" group. We will also explore potential mediators and moderators (HIV stigma, depression, level of drug use, social support). Outliers will be assessed using standardized residuals; if necessary, analyses will be accomplished for all data as well for non-outlying cases only.

Acceptability and feasibility will be analyzed using survey items and objective measures (opened text messages, prescription pick-up). Quantitatively we will assess each feasibility and acceptability measure in both groups by inspecting trajectory plot of mean levels of satisfaction over time. No formal testing is proposed except for the descriptive statistics summarized at each follow-up assessment. We will also explore associations between participant characteristics and acceptability in order to identify subgroups of participants for whom the intervention may be less acceptable. Qualitative data will be collected via open-ended answers on the mid-intervention, post intervention and three month follow-up survey. This data will be analyzed using the Krueger method of analyzing narrative data. A thematic framework will be developed to create categories and quotes will be indexed according to categories to reduce data. Charting of quotes to

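### Separate baseline-adjusted models at months three and six would drop about 17 of 68 women from the secondary-scale comparison at month three; loss that differs by arm could bias it modestly

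*Combined protocol and SAP*

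**What the plan says.** The Secondary outcomes paragraph is the same in the protocol's Analysis Plan and in the SAP. It names self-efficacy, PrEP attitudes and decisional conflict as continuous measures. Linear models relate arm to decisional conflict, self-efficacy and "PrEP attitude scales at month three and three months post intervention", and "baseline outcome measures will be adjusted as covariate in the model development". Month one does not appear. The paragraph's only data-handling rule concerns outliers. Neither document names an analysis population, a missing-data method or a sensitivity analysis for dropout.

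The Sampling section plans 68 women, "assuming a 75% retention rate at the end of the intervention, leaving us a final study sample of 50". No retention figure is given for the follow-up three months later.

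The protocol points two ways on what is asked at month one:

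- The Randomized Pilot section lists surveys at the start, one month, three months and follow-up. It then says "Demographic information will be collected along with perceptions of PrEP, decisional conflict, and self-efficacy", without tying that content to particular visits.
- Procedure Phase 3 describes the one-month contact as "completing a quick assessment of adherence and acceptability of the intervention", and the Attachments list titles the mid-intervention instrument (F) an adherence survey.

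Procedure Phase 3 also sets different contact by arm. Enhanced counsellors reach out and arrange at least monthly appointments, with weekly texts. Basic counsellors meet women at the start and over the next three weeks and are then available on request; Basic texts are bi-monthly.

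**The concern.** A linear model for the month-three score can use only women who have one. With a quarter of the sample expected to be gone by then, a comparison of all randomised women becomes a comparison of those who stayed. The plan's reference to a final sample of 50 fits that reading.

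Baseline adjustment removes bias from loss that depends on the baseline score. It does not remove bias from loss that depends on how a woman felt after baseline, if that dependence or the amount of loss differs between arms. The arms differ by design in how actively women are contacted, so such a difference is plausible.

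The SAP treats greater movement in PrEP attitudes in the Enhanced arm as a sign of promise, and says positive results will support a full trial. A contrast that shifts with retention is a weaker guide to that decision.

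**Working it through.** **1. The plan's own figure.** From Sampling: 68 enrolled, 75% retained at the end of the intervention.

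- Retained: 68 × 0.75 = 51, against the stated 50; the figure reproduces within one woman.
- Lost by month three: 68 × 0.25 = 17 (or 68 − 50 = 18).

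**2. Month six.** The documents give no figure. At assumed retention of 65%, 56% or 50%, 44, 38 or 34 women remain, so 24, 30 or 34 are lost. If nobody leaves after month three, the loss stays at 17.

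**3. Size of possible bias at month three.** All inputs here are assumptions except 34 per arm (68 ÷ 2).

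- Scores at baseline (Y0), month one (Y1) and month three (Y3) are normal with SD 1 and common correlation 0.6; higher is better.
- Loss occurs after month one. Probability of staying: logit = 1.8 in Enhanced; logit = 0.85 + 1.2 × Y1 in Basic. This gives retention of about 86% and 66%, averaging (86 + 66) ÷ 2 = 76%, close to the plan's 75%.
- Planned model: Y3 = a + b × arm + c × Y0, in women with Y3. Bias = mean of b − true effect.
- Comparator: a likelihood estimate from the regression of Y1 on arm and Y0, combined with the regression of Y3 on arm, Y0 and Y1. With this pattern of loss it is equivalent to a mixed model with baseline as covariate.
- 4,000 simulated trials per scenario.

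| True effect (SD) | Planned model | Using month one | Standard error, both |
|---|---|---|---|
| 0.50 | 0.42 | 0.50 | 0.23 |
| 0 | −0.08 | 0.00 | 0.23 |

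The bias is 0.42 − 0.50 = −0.08 SD, about a third of the standard error (0.08 ÷ 0.23 = 0.35). For correlations of 0.5 to 0.7 it stays near 0.07 to 0.08 SD.

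**4. Other patterns of loss, no true effect, planned model.**

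- Same dependence on Y1 in both arms, unequal amount of loss: −0.04 to −0.05 SD. A separate large-sample run with 15% against 35% loss gave −0.06.
- 25% loss per arm, dependence in one arm only: 0.07 to 0.08 SD in size.
- 25% loss per arm, dependence in opposite directions: 0.15 SD, an extreme case.
- Same rate and same pattern in both arms: 0.00 SD.

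**5. How much a month-one score would recover**, starting from the −0.08 SD scenario.

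- Every woman attends month one: 0.00 SD remains.
- Half of those later lost also miss month one: −0.03 SD remains.
- All of those later lost miss month one: −0.08 SD remains, so nothing is corrected.
- Separately, if loss depends on the month-three score itself: about −0.21 SD with the planned model and −0.18 SD with the mixed model.

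**The case against.** The case for leaving the plan alone has substance.

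- **Survey contact is the same in both arms.** Procedure Phase 3 has study staff, not only counsellors, contact women for the month-one, month-three and follow-up assessments, without distinction by arm. Compensation is identical ($20 at month three, $50 at follow-up). This stands. It makes strongly unequal loss less likely, but does not remove the difference in outreach and texting. The 86% and 66% retention figures have no source in the documents.
- **The bias is small and need not favour the intervention.** In the main scenario coverage of the 95% interval stays at 93 to 94%, root mean square error is 0.24 against 0.23, and the error runs against Enhanced. This stands, and limits the weight of the point. These are secondary outcomes in a pilot that seeks directional insight.
- **Month-one scores may never have been planned.** A reader might infer that the plan collects them and discards them. The documents do not support that. The Randomized Pilot sentence names no visit, while the description in Procedure Phase 3 and the title of Attachment F suggest adherence and acceptability only. The attachment is not in the text available, so the question stays open.
- **Per-visit baseline-adjusted models are standard.** True with few missing scores. With a quarter of women expected to be missing and no method stated, a model that uses every observed score is a better choice at little cost, and more than a matter of taste.

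**Conclusion.** The point holds in limited form. About 17 of 68 women would drop out of the month-three comparison of the three secondary scales. This assumes that the linear models are fitted to women with observed scores, which the plan implies but does not state. Bias of about 0.04 to 0.08 SD, against a standard error of 0.23, is possible if loss is related to the scores and its amount or pattern differs by arm. It is nil if rate and pattern are the same.

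Three stronger readings should be avoided:

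- That selective loss does bias the comparison: the documents make differential loss plausible and do not show it.
- That 25% is also the planned loss at month six: the figure is tied to the end of the intervention only.
- That a mixed model would bring back all 68 women: with baseline as a covariate, a woman with no post-baseline score contributes nothing, and month-one attendance is not stated.

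The point concerns the three scales only, not the adherence outcomes or the descriptive satisfaction plots.

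**What to change.** 1. Reconcile the Randomized Pilot section with Procedure Phase 3 and the title of Attachment F, and state whether the three scales are asked at month one.
2. In both copies of the Secondary outcomes paragraph, replace the separate models with one repeated-measures mixed model per scale. Outcomes are all post-baseline scores collected: months three and six, plus month one if asked. Terms are baseline score, arm, visit and arm-by-visit. Report the arm difference at months three and six.
3. If the scales are not asked at month one, add multiple imputation by arm for all randomised women, with month-one adherence and weekly medication pick-up, both already recorded, as auxiliary variables.
4. Report retention by arm at each assessment.

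The cost is SAP wording and some extra programming. If the sponsor chose to add the scales at month one, it would also cost a few survey minutes. In the simulation the standard error did not rise. The limit should be stated in the SAP: these methods correct only loss that observed data predict, and add nothing for women with no post-baseline data.
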